1.0 Study Objectives

The objectives of the "Safety and Feasibility of Cultivated Autologous Limbal Epithelial Cell (CALEC) Transplantation in the Treatment of Limbal Stem Cell Deficiency" study are as follows.

Excerpt from Protocol Section 2:

The main aim of the study is to preliminary estimates of the safety and feasibility of cultivated autologous limbal epithelial cell (CALEC) transplantation in the treatment of unilateral LSCD. Secondarily, efficacy of CALEC will be investigated and both safety and efficacy of CALEC will be compared to CLAU. These secondary objectives are intended to be exploratory rather than conclusive.

PRIMARY OBJECTIVES

- 1. Safety (within CALEC group): To establish the safety of CALEC transplantation by determining the incidence of primary ocular adverse events through 18 months of follow-up.
- 2. Feasibility (within CALEC group): To establish feasibility of manufacturing CALEC for corneal surface reconstruction.

SECONDARY OBJECTIVES

- 1. Safety (CALEC versus CLAU): To investigate whether CALEC is similar to standard treatment with CLAU by comparing incidence of primary ocular adverse events through 18 months of follow-up
- 2. Efficacy (within CALEC group): To investigate whether CALEC transplantation is efficacious in treatment of LSCD participants by comparing pre-operative to post-operative clinical parameters at months 3, 12, and 18.
- 3. Efficacy (CALEC versus CLAU): To investigate whether CALEC is similar to standard treatment with CLAU by comparing between-group changes from pre-operative to post-operative clinical parameters at months 3, 12, and 18.

STUDY CONCLUSIONS

The results of this Phase I/II study will provide guidance on whether to continue to a larger Phase III study and will also provide preliminary data to help determine sample size for future trials. Generally, if the study is not halted for feasibility issues, and there are no major safety or efficacy trends that favor CLAU, a larger study of CALEC could be considered. However, caveats of the study data and other potential factors outside of the trial will need to be considered and weighed in the ultimate decision of whether to proceed.

13 14

15

16

17

18

Treatment assignment will have two sequential phase – Phase A followed by Phase B. Phase A is non-randomized; all patients will receive CALEC treatment (investigational arm). Phase B is randomized; patients will be randomly assigned to CALEC or CLAU in a 2-to-1 ratio. The goal of Phase A is to establish initial safety and feasibility of a few CALEC cases prior to initiating the randomized Phase B. The sample size determination accounts for these 2 phases.

19

2.0 Study Outcomes

20 21

Excerpt from Protocol Section 7:

22 23

PRIMARY OUTCOME MEASURES
SAFETY MEASURES

Safety will be assessed in both the CALEC and CLAU groups. The occurrence of the following adverse events at any time during the 18 months of follow-up in the recipient eye will serve as the **primary safety** events of interest:

- 1. Ocular infection (defined as endophthalmitis or microbial keratitis [bacterial, fungal, parasitic])
- 2. Corneal perforation
- 3. Graft detachment ≥50%

In addition to the primary safety events, all adverse events (systemic and ocular in donor and recipient eyes) will be captured. The severity of each adverse event and the relationship of the event to the cell therapy procedure will be assessed by an independent Medical Monitor(s) (MM). The independent Medical Monitor's (see Section 9.3) coding of the adverse event and designation of severity and relatedness to treatment will serve as final to use for adverse event reporting and safety outcome analysis.

FEASIBILITY MEASURES

Manufacturing feasibility will be evaluated in the CALEC group, for each biopsy attempt. At least one CALEC construct will be attempted to be manufactured from each biopsy, as detailed in the MOP. Each attempted construct will undergo Quality Control (QC) testing to determine product conformity to CMCF release criteria per MOP, which includes assessments of cell growth, cell viability, and culture contamination. If all of these QC release criteria are met for at least one CALEC construct, the biopsy attempt is considered a feasibility success.

In the event that a construct met all QC release criteria, but surgery was not performed for a reason unrelated to the development of construct for transplant, the case would still be considered a feasibility success for the biopsy attempt.

Up to two biopsy attempts of a single participant may be performed according to Section 5. Feasibility analysis will explore both the number of biopsies per participant and the number of construct attempts per biopsy, and whether those construct attempts met QC release criteria. Each of the individual QC testing and acceptance criteria will be documented to further describe constructs that did not meet the criteria for release.

SECONDARY OUTCOME MEASURES

Efficacy Measures: Efficacy will be assessed in both CALEC and CLAU groups. The primary efficacy outcome will be a binary "Complete Success" of the graft, as defined below. Secondarily, "Partial Success" will also be considered according to a 3 category outcome defined below.

- 1. "Complete Success" will be defined as improvement in corneal surface integrity
- 2. "Partial Success" will be defined as
 - a. No improvement in corneal surface integrity and
 - b. Improvement in either
 - i. Extent of corneal vascularization or
 - ii. Participant symptomatology
- 3. Otherwise, not a success

Improvement in each area is defined as follows, where changes are measured relative to the Baseline visit:

- Corneal surface integrity
 - o Decrease in epithelial defect surface area (based on clinical assessment by an independent investigator, not the treating surgeon, as described in the MOP) by ≥75% or
 - o Decrease in corneal surface staining (based on clinical assessment by an independent investigator, not the treating surgeon, using NEI grading scale) by ≥50%
- Extent of corneal vascularization
 - Decrease in neovascular area (based on digital slit lamp photographs, using mathematical software to calculate as described in the MOP) by ≥25%
- Participant symptomatology

- o Decrease in Ocular Surface Disease Index (OSDI) score by ≥25% or
- o Decrease in Symptom Assessment in Dry Eye (SANDE) score by ≥25%

The primary efficacy time points will be at 3 months (to assess early success), as well as 12 and 18 months (to assess late success). Efficacy outcomes at all interim post-3 month time points will also be evaluated secondarily.

OTHER OUTCOME MEASURES

In addition to the primary and secondary outcome measures defined above, distribution of data and summary statistics will be evaluated on the following in both groups at each time point where relevant data are collected: IOP, impression cytology, corneal opacification, visual acuity. All reported adverse events will also be tabulated in both groups.

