- 57 limbal autografts (Haamann et al., 1998, Tan et al., 1996, Kenyon and Tseng, 1989). Cases of
- 58 corneal haze, pseudopterygium, epithelial defects and conjunctivalization in the donor eye have
- 59 been reported (Dua et al., 2010, Morgan and Murray, 1996, Fogla and Padmanabhan, 2005,
- 40 Yao et al., 2002). Although recently some attempts have been made to use a smaller graft, such
- as Simple Limbal Epithelial Transplantation (SLET), there are only limited data, especially
- 62 regarding long-term follow-up on the new procedure (Sangwan, 2012).
- 63

64 In order to circumvent risks of allograft rejection (as seen in limbal allografts) and damage to the 65 donor eye (as seen in limbal autografts, such as CLAU), a technique has been developed to 66 cultivate autologous limbal epithelial cells (CALEC) for transplantation. This technique is 67 advantageous because of its ability to utilize a small amount of the participant's own tissue. The 68 risk of damage to the donor eye is bypassed by expanding limbal epithelial (stem) cells from a 69 small biopsy (2-3 mm²) onto the substrate, such as amniotic membrane, in culture before 70 transplantation. The success of using such a new surgical approach has been reported in 71 several human studies (Koizumi et al., 2001, Rama et al., 2010, Sangwan et al., 2005, Schwab 72 et al., 2000, Shimazaki et al., 2007, Shortt et al., 2007, Basu et al., 2012, Baradaran-Rafii et al., 73 2010, Nakamura et al., 2006, Pellegrini et al., 1997).

74

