75 The general advantages of CALEC transplantation are that 1) it provides an amplified source of 76 epithelial (stem) cells as compared to transplantation of the similar size of limbal biopsy, 2) it is 77 an autologous source of cells and does not carry risk of immunologic rejection, 3) it carries 78 significantly lower risk of inducing LSCD in the donor eye, and 4) it is possible to repeat the 79 biopsy and transplant owing to the non-invasiveness of the procedures to both donor and 80 recipient eyes. Currently there are no good options for treatment of LSCD in the U.S and 81 patients have a significant burden from the disease. That, along with recent advances in stem 82 cell research provide compelling reasons for conducting a study aimed at assessing first, the 83 safety and feasibility of CALEC grafts, and additionally, their effectiveness in treating LSCD. 84 85 The most common substrate utilized for ex vivo expansion of limbal epithelial cells has been 86 amniotic membrane. Amniotic membrane transplantation (AMT) has extensive history in ocular

87 surface reconstructive surgery and its utility alone or in combination with limbal stem cell

- transplantation has been reported (Holland and Schwartz, 2000, Koizumi et al., 2000, Kolli et al., 2010, Nakamura et al., 2003, Prabhasawat et al., 2001, Shimazaki et al., 2002). In cases of
- 89 al., 2010, Nakamura et al., 2003, Prabhasawat et al., 2001, Shimazaki et al., 2002). In cases of 90 partial LSCD, AMT alone has been shown to provide a useful substrate for regeneration of the
- 90 partial LSCD, AMT alone has been shown to provide a useful substrate for regeneration of the 91 remaining epithelial cells by enhancing epithelial cell migration and creating a hospitable

92 microenvironment mimicking limbal stem cell niche (Grueterich et al., 2003, Tseng, 1989, 93 Dietrich-Ntoukas et al., 2012, Shahdadfar et al., 2012, Tsai and Tsai, 2010, Tseng et al., 2002). 94 In addition, use of amniotic membrane as a substrate for limbal epithelial cell growth has added 95 the benefits of amnion's ability to facilitate epithelialization (Lee and Tseng, 1997, Tsai and 96 Tseng, 1988), reduce inflammation and scarring (Fernandes et al., 2005, Prabhasawat et al., 97 2001), and act as a new and natural basement membrane when the underlying stromal tissue 98 has been destroyed. 99 100 Combining the expansion of cells ex vivo with cultivation on an amniotic membrane has the

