5.2.3. EXCLUSION BASED ON DONOR EYE

- Conjunctivalization of the cornea defined by fibrovascular pannus more than 2mm from the limbus into the cornea for ≥3 clock hours
- Lack of limbal palisades of Vogt for ≥3 clock hours
- History of allo-limbal transplantation
- Severe dry eye disease as determined by Schirmer's test ≤5 mm
- 247 248

251

249 **5.2.4. EXCLUSION BASED ON RECIPIENT EYE**

• Severe dry eye disease as determined by Schirmer's test ≤2 mm

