 444
 444
 444
 444
 444
 444
 444
 444
 444
 444
 444
 444
 444
 444
 444
 444
 444
 444
 444
 444
 444
 444
 444
 444
 444
 444
 444
 444
 444
 444
 444
 444
 444
 444
 444
 444
 444
 444
 444
 444
 444
 444
 444
 444
 444
 444
 444
 444
 444
 444
 444
 444
 444
 444
 444
 444
 444
 444
 444
 444
 444
 444
 444
 444
 444
 444
 444
 444
 444
 444
 444
 444
 444
 444
 444
 444
 444
 444
 444
 444
 444
 444
 444
 444
 444
 444
 444
 444
 444
 444
 444
 444
 444
 444
 444
 444
 444
 444
 444
 444
 444
 444
 444
 444
 444
 444
- 450 3. The eye that is to be biopsied will be marked as such and the other eye will be covered.
- 451 4. Fluoroquinolone and proparacaine drops will be administered 3 times prior to the procedure.
- 452 5. Lidocaine 1% gel will be administered into the eye and the eye will be closed with tape.
- 4536. The participant will be brought to the operating suite and positioned in a supine position454454 under the operating microscope in the manner typical for ophthalmic surgery.
- The operative eye will be cleaned using 5% Betadine solution per standard surgical
 protocol. Both the cul-de-sac and the eyelashes will be cleaned.
- 457
 8. Under sterile conditions, a limbal biopsy of 3mm-by-3 mm (1 clock hour) will be dissected
 458
 459
 actual size of the graft will be measured and captured for data collection.
- 460
 9. The biopsied material will be placed into the container with HypoThermosol® FRS for
 461
 461
 461
 461
- 462 10. The biopsied site in the conjunctiva will be closed using interrupted sutures and/or fibrin glue463 per the surgeon's discretion..
- 464 11. Maxitrol or Tobradex ointment or drops will be placed onto the eye, if patient has no known 465 allergy.
- 466 12. Either a patch or shield will be placed over the eye.

467 **6.2.2.2. CALEC PROCEDURE – TRANSPLANTATION**

- 468
 469
 469
 469
 470
 470
 469
 470
 470
 470
 470
 470
 470
 470
 470
 470
 470
 470
 470
 470
 470
 470
 470
 470
 470
 470
 470
 470
 470
 470
 470
 470
 470
 470
 470
 470
 470
 470
 470
 470
 470
 470
 470
 470
 470
 470
 470
 470
 470
 470
 470
 470
 470
 470
 470
 470
 470
 470
 470
 470
 470
 470
 470
 470
 470
 470
 470
 470
 470
 470
 470
 470
 470
 470
 470
 470
 470
 470
 470
 470
 470
 470
 470
 470
 470
 470
 470
 470
 470
 470
 470
 470
 470
 470
 470
 470
 470
 470
 470
 470
 470
 470
 470
 470
 470
 470
 470
 470
 470
 470
 470
 470
 470
 470
 470
 470
 470
 470
 470
 470
- 471
 472
 472
 473
 474
 474

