5.0 Statistical Analysis Plan

Safety Analysis

 Coding of all adverse events for analysis will be based on the MedDRA coding determined by the Medical Monitor. The following safety analyses will be performed.

1. Primary Safety Analysis (within-CALEC group evaluation of primary safety outcomes):

- a. The primary safety events of interest (ocular infection, corneal perforation, and graft detachment >=50%) in the recipient eye will be summarized as the numbers and percentages (and 95% exact confidence intervals) of participants having each event and the number and percentage (and 95% exact confidence intervals) of participants having any of the three events, up to 18 months.
 - These events will be evaluated in CALEC Group Phase A and Phase B participants combined. Only participants who completed transplant and only events occurring after transplant will be included.

2. Primary Safety Analysis (CALEC versus CLAU comparison of primary safety outcomes):

- a. The primary safety events of interest (ocular infection, corneal perforation, and graft detachment >=50%) in the recipient eye will be summarized as the numbers and percentages (and 95% exact confidence intervals) of participants having each event and the number and percentage (and 95% exact confidence intervals) or participants having any of the three events, up to 18 months
 - i. These events will be evaluated within each treatment group, in Phase B participants only. All participants who were randomized will be included regardless of whether transplant was completed. Phase B participants who discontinued prior to randomization will not be included. All events occurring after randomization will be included. Events prior to randomization will not be included.
- b. The two treatment groups will also be compared by computing the differences in percentages (and 95% exact confidence intervals) having each event and the difference in percentages (and 95% exact confidence intervals) having any of the three events.
- 3. Secondary Safety Analysis (explore/evaluate all adverse events): All reported adverse events up to 18 months (including systemic, recipient, and donor eye events) will be evaluated as follows.

- a. Within each MedDRA system organ class, tabulate the number and percentage of participants having at least 1 event within the given system organ class. Evaluate both of the following ways:

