 - i. Within-CALEC group: Evaluate in CALEC Group Phase A and Phase B participants combined. Only participants who completed transplant will be included. Only events occurring after transplant will be included.
 - ii. CALEC versus CLAU comparison: Evaluate within each treatment group, in Phase B participants only. All randomized participants will be included regardless of whether transplant was completed. Phase B participants who discontinued prior to randomization will not be included. All events occurring after randomization will be included. Events prior to randomization will not be included.
- b. Within each adverse event term (MedDRA lower level term), tabulate the number of events and number of participants with at least 1 event, separately for systemic, recipient eye, and donor eye events. Evaluate the data in both of the following ways:
 - Within-CALEC group: Evaluate in CALEC Group Phase A and Phase B participants combined. Only include participants who completed transplant and only include events occurring after transplant.
 - ii. CALEC versus CLAU comparison: Evaluate within each treatment group, in Phase B participants only. All participants who were randomized will be included regardless of whether transplant was completed. Phase B participants who discontinued prior to randomization will not be included. All events occurring after randomization will be included. Events prior to randomization will not be included.
- 4. Additional Safety Analyses for DSMC Monitoring Purposes Only:
 - a. The mean number of events per patient will be calculated as the total number of events reported in the treatment group, divided by the total number of patients in the treatment group. Evaluate the data in both of the following ways:
 - i. Within-CALEC group: Evaluate in CALEC Group Phase A and Phase B participants combined. Include only participants who completed transplant and include only events occurring after transplant.
 - ii. *CALEC versus CLAU comparison*: Evaluate within each treatment group in Phase B participants only. All participants who were randomized will be included regardless of whether transplant was completed. Phase B participants who discontinued prior to randomization will not be included. All events occurring after randomization will be included. Events prior to randomization will not be included.

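### Donor-eye harm has no named safety event, percentage or confidence interval, and the within-CALEC safety tables start at transplant, not at the biopsy that puts the donor eye at risk.

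*SAP*

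**What the plan says.** **Primary safety.** The three events (ocular infection, corneal perforation, graft detachment of at least 50%) are defined as "adverse events at any time during the 18 months of follow-up in the recipient eye will serve as the" primary safety events (SAP 2.0; same definition in Protocol 7.1.1). SAP 5.0, Safety 1 and 2, gives exact 95% intervals for each event and for any of the three.

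**Donor eye.** SAP 2.0 adds: "In addition to the primary safety events, all adverse events (systemic and ocular in donor and recipient eyes) will be captured". SAP 5.0, Safety 3, says: "All reported adverse events up to 18 months (including systemic, recipient, and donor eye events) will be evaluated as follows". Item 3.a gives numbers and percentages by system organ class, not split by eye. Item 3.b gives numbers of events and of participants per lower level term, "separately for systemic, recipient eye, and donor eye events".

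**Who and when.** The within-CALEC versions of Safety 1 and 3 include only participants who completed transplant and only events after transplant. The CALEC-versus-CLAU versions include all randomized Phase B participants, from randomization.

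**Why the donor eye matters.** Protocol section 1 gives donor-eye LSCD as the main limitation of the conventional autograft and lists among the advantages of CALEC a "significantly lower risk of inducing LSCD in the donor eye".

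**What is measured.** Donor-eye staining, defect area and fluorescein photographs are required at the post-biopsy visit (6.8.5), on Day 1 (6.8.10) and at the scheduled visits after that (6.8.11).

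**The concern.** The donor eye is the participant's better eye, and the biopsy is its only planned surgical exposure. A safety plan for this procedure would normally name at least one donor-eye harm, give its frequency with an interval, and start counting at the biopsy. This plan does none of these within the CALEC group.

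Protocol 2.3 makes a larger study depend partly on there being no major safety concerns. As written, that judgment would rest on a recipient-eye composite with an exact interval and, for the donor eye, a list of term counts that omits the weeks right after surgery. Donor-eye staining and defect area, required at most visits, would have no planned safety summary.

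**Working it through.** **1. The plan's own precision figures reproduce.** Inputs are n = 15 and exact binomial 95% limits (SAP 4.0). With zero events the upper limit is 1 − 0.025^(1/n).
- 0/15: 1 − 0.025^(1/15) = 21.8% (SAP: 22%).
- 1/15: 0.2 to 31.9% (SAP: 0 to 32%).
- Chance of at least one event at a 5% risk: 1 − 0.95^15 = 0.537 (SAP: 0.54).

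So the SAP has a working standard for reporting rare events. It applies it to recipient-eye events only.

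**2. What 3.b can and cannot give.** Dividing a term's participant count by the number transplanted gives a proportion for that term. The proportion with any donor-eye event cannot be recovered, because one participant may appear under several terms. Protocol section 1 names four donor-eye harms after limbal autograft: haze, pseudopterygium, epithelial defect and conjunctivalization. Suppose, as a hypothetical, that three terms are each reported in one of 17 participants:
- All in the same participant: 1/17 = 5.9% (exact 95% CI 0.1 to 28.7%).
- In three different participants: 3/17 = 17.6% (3.8 to 43.4%).

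The 3.b table would look the same in both cases. Item 3.a does not help, since it does not separate the eyes.

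**3. What the time window drops.**
- Transplant is anticipated 10 to 30 days after biopsy (Protocol 6.8). The within-CALEC tables start at transplant.
- Both visits with an adverse event assessment in that gap, post-biopsy (6.8.5) and pre-operative (6.8.7), fall before the tables begin.
- A second biopsy is at least 30 days after the first (5.6). A participant transplanted after a second biopsy therefore has at least 30 + 10 = 40 days from first biopsy, and two donor-eye biopsies, before counting starts.
- Participants biopsied but not transplanted are monitored for 30 days, and longer if a donor-eye complication persists (5.7). They enter no within-CALEC safety table.
- The SAP tables that start at randomization cover Phase B only and serve the CLAU comparison, which was dropped in Protocol v5.0 (section 12). Under current Phase B enrollment there is no randomization to count from.
- For a second CALEC transplant, Protocol 15.7.1 does summarise events from the biopsy onward. The initial transplant has no such rule.

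**4. Staining and defect area.** The other-outcome lists (Protocol 7.3; SAP 2.0; SAP Additional Tabulations) omit both. SAP Efficacy item 5 includes them without naming an eye, largely as percentage change from baseline: 100 × (follow-up − baseline)/baseline. That is undefined for a donor eye with no defect at Baseline.

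**5. Precision if a donor-eye event were treated the same way.** The transplant cap is 17 (Protocol 5.5).
- 0/17: 1 − 0.025^(1/17) = 19.5% upper limit.
- 1/17: 5.9% (0.1 to 28.7%).
- Chance of at least one event, 1 − (1 − p)^17. The documents give no donor-eye rate, so p is assumed: 1% gives 16%, 2% gives 29%, 5% gives 58%, 10% gives 83%.

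N for all biopsied participants may exceed 17.

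**6. Biopsy size, a separate inconsistency.** Protocol section 1 describes a "small biopsy (2-3 mm²) onto the substrate". Section 6.2.2.1 says: "Under sterile conditions, a limbal biopsy of 3mm-by-3 mm (1 clock hour) will be dissected". 3 × 3 = 9 mm², which is 9/3 = 3 to 9/2 = 4.5 times the Background figure.

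**The case against.** A reader might infer that the plan yields no donor-eye rate at all, or leaves that eye unwatched. The documents do not support either reading.
- Item 3.b lists donor-eye events separately, so post-transplant proportions per term can be derived.
- Protocol 7.3 lists visual acuity, IOP, opacification, AS-OCT limbal thickness, and IVCM cell types and palisades. AS-OCT and IVCM are taken in both eyes at Baseline and Months 12 and 18 (6.6.10, 6.6.11) and are close to the harm of interest. The list does not say the eyes will be shown separately, and the SAP omits AS-OCT and IVCM.
- The slit-lamp examiner is not the operating surgeon (6.6.4). An independent Medical Monitor has the final decision on coding, severity and relatedness, though only for reported events. The DSMC's expedited events are specified by eye (SAP Safety 4.b).
- Biopsy-period events are collected: the SAP Appendix says all adverse events after baseline are collected and reported. The gap is in analysis, not capture.

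Nor is the donor eye examined at every visit. The pre-operative list is recipient eye only (6.8.7), and the Week 2, Month 9 and Month 15 visits are optional where travel is prohibitive (6.8).

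It is also fair to say that lower donor-eye risk is background rationale, not an objective, that 2.3 is not limited to primary events, and that the choice of primary events is a design decision. This answers any demand to make a donor-eye event primary. It does not answer the missing summary or the late start of counting. The Background biopsy size may describe the technique in general, and the discrepancy does not itself show an analysis gap.

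**Conclusion.** The point holds in this form: the plan collects donor-eye harm but does not summarise it. Within CALEC there is no named donor-eye event, percentage, interval or any-event total, no safety summary of donor-eye staining or defect area, and no count of events between biopsy and transplant or in biopsy-only participants. The window is the more serious part, because it removes the period right after the donor-eye surgery.

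It should be corrected, but it does not undermine the primary recipient-eye analysis. The correction would describe donor-eye safety, not confirm a low risk: with no events in 17 the data remain compatible with a risk of 19.5%. This assumes 17 participants, the transplant cap. The 58% chance of seeing at least one event rests on an assumed 5% risk; the SAP's own 5% refers to recipient-eye events.

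**What to change.** In SAP 5.0, Safety:

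1. Count donor-eye adverse events from the date of first biopsy in all biopsied participants. Give n/N and exact 95% CI for any donor-eye event and for each term. Tabulate biopsy-to-transplant events separately, and biopsy-only participants separately, since the latter have only about 30 days of monitoring.
2. Among transplanted participants, give n/N with exact 95% CI for a donor-eye epithelial defect (as defined in Protocol 6.6.4.2) at Month 1 or later, and donor-eye NEI score change from Baseline. Biopsy-only participants do not belong in this denominator, because Month 1 is timed from transplant. State that the Protocol 7.3 visual acuity, AS-OCT and IVCM summaries are given separately by eye.
3. Optionally, add as an event a donor eye that newly meets a limbal criterion of Protocol 5.2.3: "Conjunctivalization of the cornea defined by fibrovascular pannus more than 2mm from the limbus into the cornea for ≥3 clock hours", or palisade loss over the same extent.

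Report these beside the recipient-eye composite when 2.3 is applied, labelled descriptive.

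Cost: items 1 and 2 need SAP wording only and use data already collected. Item 3 needs a form field for clock hours at existing slit-lamp examinations, because the listed follow-up items are opacification and staining.

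Separately, the biopsy sizes in Protocol sections 1 and 6.2.2.1 must be reconciled.
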